## 2.2 Biomedical Research Methods and Diagnostic Markers

Biological research methods such as genetics and proteomics are beginning to develop a powerful influence in developing new medicines and diagnostics, which is an emerging area of biomarker development. Biomarkers are substances that can be found in the body when cancer is present. The classic tumor marker is a protein that can be found in the blood at increased levels when a certain type of cancer is present. Systemic Lupus Erythematosus can be detected from values of biomarkers present within a person's blood. In recent years, doctors have begun to develop newer types of biomarkers using different types of biological and genetic material. Bioinformaticians and molecular biologists have deemed this field of biomarker discovery using the suffix "*omics*." Examples of *omics* include *genomics*, *proteomics*, *metabolomics*, and *pharmacogenomics*.

The study of patterns of DNA changes (or mutations) is called *genomics*. We know that most health conditions have changes in DNA that direct the function of cells. By looking for DNA aberrations in blood samples, scientists may find complex genetic patterns that characterized certain health conditions. *Pharmacogenomics* analyzes an individual's response to certain drugs by looking at their genes. Such analysis will help physicians choose the optimal treatment course for each participant maximizing drug efficacy while simultaneously minimizing adverse effects, truly personalizing medicine.

Another approach, called *proteomics*, looks at the patterns of all the proteins in the blood instead of looking at individual protein levels. New testing equipment allows researchers to look at thousands of proteins at one time. It is unlikely that such a test would be used in the clinic, but it may help researchers narrow down which protein levels are important in a certain disease state. This information could then be used to develop a diagnostic test looking only at these important proteins. Alternatively, treatment may be developed to target these proteins affecting the

pathophysiology of a condition or to test the efficacy of a certain therapy used in a case. These new testing methods are still in the early stages of development. Very few are in routine use at this time.

*Metabolomics* studies the chemicals and molecules created during specific cellular processes (metabolites). Metabolomic profiles can capture a cell's physiology at a specific time. Metabolites are much smaller than proteins. Therefore, *metabolomics* allows researchers to view a broader range of chemicals within the molecular spectrum. Working together with *proteomics*, researchers can put together a complete picture of cellular pathways utilized by health conditions. The *omics* field of biomarker discovery is but one new field currently explored by biomedical researchers. The concept of statistically analyzing a vast amount of data for patterns within whole populations is also an expanding area of interest for a couple of reasons. Such studies can be performed remotely on an electronic dataset by multiple investigators without depleting the physical biospecimen. Potential research studies for which Sanguine BioSciences, Inc., will provide biospecimens are not limited to the types of research discussed above. Instead, the purpose of the above discussion is to elucidate potential areas of future research to which biobank samples may be provided.

### 2.3 Study Rationale

The availability of high-quality biospecimens to use in such studies dictates the quality of scientific results achieved and remains a significant roadblock to the standardization of results in biomedical research. Following the accepted international best biorepository practices, Sanguine Biosciences, Inc. will provide superior biospecimen collection and processing to the research community. By following these practices, specimens will be a consistent grade to promote viable and reproducible scientific results. The primary purpose of SAN-BB-02 is to collect, preserve and/or distribute quality biospecimens with associated health data (annotations) to researchers. Not only will this study physically accomplish this task, but Sanguine Biosciences, Inc., will also establish an electronic DNA database. Through physical and electronic biospecimen collection, this study will create a shared research infrastructure for a large population of investigators, thus allowing them access to physical biospecimens, electronic genetic material, and associated health data. This dual method of biospecimen availability allows studies to fully explore their research initiatives with a direct emphasis on clinical impact.

Sanguine Biosciences, Inc., is a steward of health information, physical and electronic, biological and subjective, and provides a direct resource of molecular data for researchers via biological tissue collections and electronic genetic library. Sanguine BioSciences, Inc., will source potential participants using different public spheres to collect a diverse genetic and epigenetic cohort allowing for potential population-based investigations to discern general molecular trends in multifactorial conditions. Such wide-range studies can only be qualitatively accomplished by comparing a large condition-specific population against a diverse control population where biospecimen integrity is standardized across all samples. The core competency of this study is providing such samples to the research community to ensure quality results. Through valid population-based studies, personalized medicine can truly come into focus in the clinic. Individuals can be compared against molecular trends within a population to be diagnosed and treated according to molecular disposition instead of gross, histological, or clinical standards of

care currently in use.

### **3 STUDY OBJECTIVES & PURPOSE**

The primary study objective is to collect, preserve, and/or distribute annotated biospecimens and associated medical data to institutionally approved, investigator-directed biomedical research to discover and develop new treatments, diagnostics, and preventative methods for specific and complex conditions.

To further study genotypic and phenotypic characteristics of specific and complex health conditions, the Sponsor may establish its biorepository to facilitate viable experimental results by supplying the research community with consistent, high-quality specimens. Sanguine BioSciences, Inc. (hereinafter, Sanguine) may collect biospecimens from health conditions participants and controls participants. Peripheral blood mononuclear cells (PBMC), serum, DNA/RNA, protein, and other blood portions may be extracted from blood samples and stored for future research. Other biospecimens that may be donated and stored include but are not limited to saliva, sputum, urine, hair, skin, nail clippings, stool, and semen. Demographically matched control samples may be collected to give researchers a baseline to compare against health condition samples. Control donors are considered participants who have not been clinically diagnosed with a medical condition.

Eventually, Sanguine may develop participant-derived induced pluripotent stem cells (iPS cells) to develop disease-specific cell lines that can be expanded in culture for research and development purposes only. The cells that we would obtain from participants blood do not divide in culture, and therefore will be available to a limited number of researchers. However, one can genetically transform those cells to divide. These cells are very similar to embryonic stem cells (cells that divide and transform into all types of cells – like nerve cells, skin cells, etc.)—allowing more of the participants cells to researchers working in specific conditions. The advantage of iPS cells – which are very similar to embryonic stem cells – is that they are not derived from human embryos, eliminating the ethical concern. By providing these samples to researchers, Sanguine will facilitate the pre-clinical analysis and correlation of genotypes with phenotypes (such as clinical outcomes).

The Sanguine biorepository may store biospecimens extracted from blood samples donated from control and health condition donors for unspecified future biological and biomedical research. The information gathered from this future research potentially include, but is not limited to:

- DNA/RNA/protein mutation analysis;
- DNA methylation analysis;
- Protein to DNA/RNA binding analysis; and/or
- Gene/protein expression analysis.

The additional information may help improve participant care by developing new diagnostics and therapies. The information will also help physicians understand how and why specific treatments behave differently in different participants, leading to individualized drug therapy for participants in the future.

Sanguine may also extend the biobank to include an electronic genetic database composed of

partial and whole sequences of the participants DNA and RNA. Such a library would allow more researchers to utilize the biobank samples than possible through traditional physical biobanking means.

## 4 STUDY DESIGN

### 4.1 Study Design Rationale

Researchers with institutionally approved study initiatives may request and analyze the biospecimens, genetic material, and health data collected in this study to better understand specific health problems.

The information from this unspecified future biological and biomedical research may facilitate developing new diagnostic tools and personalized treatments for specific health conditions. Such conditions may be acute or chronic, specific or complex, prevalent or rare. Many health conditions overlap with each other clinically and genetically, necessitating in-depth molecular characterization of these conditions to diagnose and treat sufferers of such conditions successfully. Sanguine will facilitate these research endeavors by providing samples of standard quality collected during this study to research institutions.

The biobank may potentially collect biospecimens from rare populations such as elderly participants up to 85 years old. As the American population ages, the Sponsor feels that research on the aging process and conditions and diseases that disproportionately affect the elderly becomes increasingly important.

Other rare and underrepresented populations in research from which the study aims to collect include participants with infectious diseases, including, but not limited to, HIV/AIDS and hepatitis subjects. Because this is a potential population from which biospecimens may come, special training, consideration, and safety will be performed by study staff handling such specimens. Since it is considerably more dangerous to handle specimens with bloodborne pathogens present, many biorepository studies neglect to collect these populations. Unfairly neglected and underrepresented within many biorepository cohorts, the Sanguine's biobank wishes to collect and store quality infectious specimens to help advance biomedical research of such diseases.

The study may require a tissue collection and/or a participant survey for participation. Most tissue collected will come from a blood draw; up to 100mL for the health condition group, 60mL for the exceptive condition group, and up to 180mL for the control group (if determined safe for the participant). Participant surveys may involve participant reported outcomes (PROs) or custom participant surveys.

Drawing up to 100mL for the health condition group will allow the biobank to collect enough blood from isolating several sub-products from the whole blood, such as serum, plasma, peripheral blood mononuclear cells (PBMCs), and genetic material (DNA/RNA), which are commonly used in biomedical research. A blood draw will provide biological tissue to research and expose participants to minimal risk. A blood draw allows participants flexibility in scheduling the draw, either at a site or in the comfort of their home.

Due to a potential increase of phlebotomy risks for people with certain medical conditions such as cardiovascular diseases, bleeding disorders and late-stage kidney problems, the exceptive condition group will have only up to 60mL drawn to minimize these risks.

The study aims to collect biological tissue from multiple populations to support and advance biomedical research. Drawing a large volume of blood from healthy donors will provide more control biosamples for researchers (posing minimal risk to the participant). Allowing the study efforts to concentrate on collecting samples from various populations to service more research fields.

The control group may have up to 180mL of blood drawn for the study if determined that the participants health will not compromise their safety during the draw. The amount of 180mL is about one-third of the blood drawn during a blood donation and is considered by the Department of Health and Human Safety (HHS) to pose minimal risk to the participant. The study would like to have the potential to draw up to 180mL if the health of the participant allows this amount biological tissue to be collected from one appointment. Since the major risk and discomfort from venipuncture comes from being stuck with the needle, the study believes that a one-time blood draw of a larger volume would be potentially more comfortable for a healthy individual versus undergoing multiple venipunctures.

Participant health will be assessed prior to phlebotomy to determine maximum blood draw volume for all cohorts.

For all research requests that are not covered within this protocol, independent protocol amendments addressing the procedural changes may be drafted to address and minimize possible study risks. A medical practitioner will review the procedural amendments for safety assessment and submit to the IRB for review.

## 4.2 Description of the Study

This protocol is for a single-site, biospecimen collection study in adult participants. Participants will sign an informed consent (or provide verbal assent if a legally authorized representative will sign the consent) before the biospecimen collection(s). In addition to the Principal Investigator (PI), trained study staff (e.g., research coordinators, and phlebotomists) can screen a potential participant to determine their study eligibility and can administer and sign the Informed Consent Form (ICF) with the participant and address all of their questions regarding the ICF and study design.

As a next step, a research coordinator will set up a potential enrollment appointment with a contracted mobile phlebotomist. Health condition, exceptive condition, and control participants will be recruited by one or any of the following resources, but not limited to:

- Use of online marketing where potential participants receive study information from the Sanguine's website or online participant referral program;
- In the site investigators (or PI's) clinic; and/or
- Through community advocacy programs.
- Participant Referral

In all cases, potential participants will not be contacted by Sanguine study staff before agreeing to Sanguine's Privacy Policy, available online, or by contacting Sanguine directly via phone or email.

Participants who have agreed to participate and who have signed the ICF for Study SAN-BB-02 (or given assent if a legally authorized representative will sign the ICF) will be eligible to

participate in this biorepository study. A signed ICF will be obtained from those participants who choose to participate. After obtaining the informed consent for this study, a professional phlebotomist, nurse practitioner, physician, or other qualified health professional will collect specified tissue samples. Blood samples will be drawn, and minimal risk tissue collection procedures may be performed at the participant's home, workplace (in a private setting), other private settings, or selected clinics.

Blood samples, serum, plasma, PBMCs, and other blood portions may be processed. Additionally, DNA and/or RNA may be extracted from the collected blood samples by Sanguine. Other biospecimens that may be donated will be stored in whole or delivered directly to requesting researchers and/or designated third parties. Biospecimens will be stored in Sanguine's biobank indefinitely or until they are exhausted.

The participant's biospecimens will be annotated with self-report or medical review health information. The biospecimens and the linked clinical data will be de-identified. End users will not have any access to unique participant identifiers.

Participants may be asked to complete a participant survey either in tandem with the biospecimen collections or following a separate, variable schedule that can be customized depending on need.

#### **4.3 Compliance with Laws and Regulations**

This study will be conducted in accordance with applicable U.S. Food and Drug Administration (FDA) and Department of Health and Human Services (DHHS) regulations, the International Conference on Harmonization (ICH) E6 Guideline for Good Clinical Practice (GCP), and applicable local, state, and federal laws. The Sponsor is responsible for personnel regulatory education in standard operating procedures and educational materials and training. The Office of Human Research Protection (OHRP) provides guidance on ethical and regulatory issues encountered in biomedical human participant's research. Sanguine strives to adhere to OHRP guidelines and compliance with DHHS Code of Federal Regulations (CFR) Title 45, Part 46 (45 CFR 46).

Laboratory compliance is consistent with national good laboratory practices and follows the International Society of Biological and Environmental Repositories (ISBER) best practice.

### **5 STUDY METHODS**

#### **5.1 Sample Size**

The number of participants to be enrolled in this study is 20,000. The reason for 20,000 participants is that the Sponsor anticipates that over 2 years of the study, at least 50% of the participants will discontinue study participation. Because this study aims to establish a tissue biorepository for future therapeutic and diagnostic research endeavors, the Sponsor requires accrual and maintenance of a large enough biospecimen cohort for research clients to obtain statistically significant results. Therefore, the Sponsor believes that this sample size will provide the required sample diversity and volume to achieve statistically significant results despite participation attrition.

Sanguine anticipates collecting biospecimens not only from participants with known health conditions but also from control participants with no known health conditions. These control biospecimens may be requested for comparison against other condition-specific biospecimens stored in the biobank. The total population of control participants is undetermined but will be included in the 20,000 total study participants.

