**STUDY DESIGN:**

- A single-site, cross-sectional study
- Biological tissue samples will be collected from study participants, processed, and preserved in the biorepository's cryogenic core biobank (hereinafter, "biobank") until a research study requests a sample.
- If a sample does not require processing, the sample may be delivered directly to the requesting researchers or designated third parties.
- Health information will be collected via self-report and medical record review to obtain a detailed clinical history of the participant's health. This information includes but is not limited to demographic and lifestyle information, current medications and comorbidities, date of diagnosis, condition-related treatment history, current disease characteristics, diagnostic reports, and family medical history.
- Sanguine will implement a software-as-a-service (SaaS) provider of electronic signature technology and transaction management solutions or a hardcopy of the informed consent form (ICF). Participants may electronically sign the ICF and authorization of release of information using an electronic device. The Sponsor may alternatively provide the participant the option of completing hardcopy documents if they so desire. In addition to the Principal Investigator (PI), approved study staff can also administer and sign the ICF and will address all of the participant's queries regarding the ICF and study design.
- All participants biospecimens, if processed, will be stored and distributed by blinded personnel to the participants direct identifiers.

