## **DURATION OF PARTICIPANT PARTICIPATION:**

- This study requires the collection of a tissue sample, which is considered active participation. Study enrollment and the sample collection take about one hour or more to complete depending on the number and types of samples collected. Therefore, active participation will be about one hour and may be up to two hours.
- Inactive participation lasts as long as a participant's samples and data remain at the biobank. There is no limit on the length of time samples and data may be stored. The samples may remain indefinitely at the biobank or until the participant decides to withdraw their participation from the study.

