### **SAMPLE SIZE CONSIDERATIONS**

The number of participants to be enrolled in this study is 20,000. The reason for 20,000 participants is that the Sponsor anticipates that over 2 years of the study, at least 50% of the participants will discontinue study participation. Because this study aims to establish a tissue biorepository for future therapeutic and diagnostic research endeavors, the Sponsor requires accrual and maintenance of a large enough biospecimen cohort for research clients to obtain statistically significant results. Therefore, the Sponsor believes that this sample size will provide the required sample diversity and volume to achieve statistically significant results despite participation attrition.

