##### **5.3.5.1 Blood Collection**

A blood draw is the most common type of biospecimen collection procedure, making up about

95% of biospecimen requests. Blood will generally be collected by venipuncture from a medical professional certified in phlebotomy. Participants may also be asked to provide a microsample of blood via fingerstick. Fingerstick samples will be collected on a blood card, such as a dried blood spot (DBS) card, or into a microtainer. Researchers may use the blood cards for specific testing of biomarkers or isolating genetic material.

Blood collection volumes are dependent on which cohort the participant is placed and self-reported medical data (see Table 1). Blood may be collected every 7 days, but the total volume collected during a 6-week period may not exceed the Table 1 volumes. Maximum blood collection volumes in Table 1 may be collected at one time

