The Sponsor allows study staff, directly and indirectly, involved with this biobank study and their family and friends to enroll and participate in the study. Since this study does not include any type of medical intervention or health care and active participation in the study is expected to be about one hour—or as long as it takes to complete the ICF process and the required biospecimen collection—undue influence or coercion of this population is minimal. All protected health information stored within the biobank database is treated with the same respect and care as all other participants. No unauthorized study staff may have access to this information, and employment status will not be influenced by information collected under this study as required by the Genetic Information Nondiscrimination Act (GINA).

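### Does expected attrition of at least 50% over 2 years, given as the reason for 20,000, contradict a cross-sectional design with one to two hours of active participation?

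*Protocol*

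**What the plan says.** The synopsis (Sample Size Considerations) and section 5.1 carry the same paragraph. Section 5.1 puts it this way: "The reason for 20,000 participants is that the Sponsor anticipates that over 2 years of the study, at least 50% of the participants" will discontinue. The synopsis likewise expects that "over 2 years of the study, at least 50% of the participants will discontinue study participation". The paragraph continues that "the Sponsor requires accrual and maintenance of a large enough biospecimen cohort for research clients to obtain statistically significant results", and ends by saying that 20,000 should give enough diversity and volume of samples despite the attrition. Section 5.1 adds that the number of controls within the 20,000 is not fixed.

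On design, the synopsis has "A single-site, cross-sectional study". On duration it says "Therefore, active participation will be about one hour and may be up to two hours", and then describes an inactive participation with no time limit, lasting while samples and data are held. Section 7.2 repeats that "active participation in the study is expected to be about one hour". Section 4.1, discussing controls, argues that a "one-time blood draw of a larger volume would be potentially more comfortable for a healthy individual versus undergoing multiple venipunctures".

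Section 5.3.5.1 allows repeat donation: "Blood may be collected every 7 days, but the total volume collected during a 6-week period may not exceed the Table 1 volumes". Sections 4.2 and 5.3.8 allow surveys on their own schedule. Section 5.8 says participation may end in part or in full. Section 5.9 gives two withdrawal routes: the bank keeps and may use what it holds, or what remains is destroyed. The first applies when the participant's wish is unclear. Both routes end the authorization to obtain records.

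**The concern.** Attrition is named as the reason for the number, not mentioned in passing, so it should fit the design. In a one-visit study the specimen is banked or shipped at enrolment, and a later departure cannot undo that. Under 5.9 it costs stored material only on a destroy request. A 50% loss of the bank would then need every leaver to ask for destruction, and enrolment would look inflated.

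The other way to make sense of the reason is a repeat-donor cohort, which 5.3.5.1 permits. Then *cross-sectional* and one to two hours seem to understate what is asked of people, and 7.2 uses the one-hour figure to argue that undue influence on enrolled staff, family and friends is minimal.

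At stake would be either the basis of the enrolment number or the statements on design and duration. A smaller worry is that a total of 20,000 cannot promise statistical significance when the control count is left open.

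**Working it through.** **Inputs.** Enrolment N = 20,000 and attrition w of at least 0.50 over 2 years (synopsis, 5.1). Retained target R: not stated. Share d of leavers who ask for destruction: not stated, so taken over its full range, 0 to 1. Alpha, power and effect size: none given, so 20,000 cannot be reproduced from a power calculation.

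**1. The plan's own figure.** With the usual inflation N = R/(1 − w), R = N(1 − w) = 20,000 × 0.50 = 10,000. This number appears nowhere in the Protocol. Since 50% is a floor, 10,000 is only an upper limit on those remaining:

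| w | remaining of 20,000 |
|---|---|
| 0.50 | 10,000 |
| 0.60 | 8,000 |
| 0.75 | 5,000 |
| 0.90 | 2,000 |

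**2. What 5.9 removes.** Donors whose specimens are not destroyed = N(1 − w·d), before any distribution or use. Enrolment needed to keep 10,000 such donors = 10,000/(1 − w·d), rounded up. At w = 0.50:

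| d | kept of 20,000 | enrolment needed for 10,000 | 20,000 minus need |
|---|---|---|---|
| 0 | 20,000 | 10,000 | 10,000 |
| 0.10 | 19,000 | 10,527 | 9,473 |
| 0.25 | 17,500 | 11,429 | 8,571 |
| 0.50 | 15,000 | 13,334 | 6,666 |
| 1 | 10,000 | 20,000 | 0 |

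**3. Sensitivity to the floor.** At w = 0.75 and d = 1, donors kept = 20,000 × 0.25 = 5,000, and the enrolment needed for 10,000 is 10,000/0.25 = 40,000. So even the sign of the surplus depends on two unstated quantities (R and d) and on one that is only bounded below (w).

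**4. Duration.** A 7-day interval allows draws on days 0, 7, 14, 21, 28 and 35, that is 6 in 6 weeks. Multiplying gives 6 × 1 to 6 × 2 = 6 to 12 hours against the one to two hours stated. This is a ceiling on a permission. The total volume stays under the Table 1 cap, and that cap may be used up in one draw. The hour or two in the synopsis also covers enrolment as well as collection, and no section says consent is repeated at each draw.

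**5. The supporting passages in context.** The 4.1 sentence defends taking up to 180 mL from a healthy control at one appointment; it does not say that participants attend once. In 7.2 the hour is the time for consent and the required collection, and 5.3.5 requires only one type of tissue collection. Neither passage excludes later, optional contact.

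**The case for a change.** The strongest case for a change is that the stated reason cannot be made to work from the Protocol's own definitions. Active participation is over in an hour or two, so a 2-year rate has no meaning for it. Inactive participation lasts while samples are held, so a donor who leaves under the keep route is arguably still in it, and only destruction counts as loss. Nothing makes 50% plausible as a destroy rate. Surveys do not help, because 5.1 speaks of biospecimens. If repeat donation is what attrition erodes, the synopsis should say so.

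Much of this stands. *Discontinue* is not defined, no retained number is given, and the attrition figure does not by itself support 20,000. *Cross-sectional* fits poorly with collection every 7 days, and the synopsis, which has samples held until withdrawal, is looser than 5.9.

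What does not stand is that the statements exclude one another. A donor with one short visit can still leave within 2 years. Leaving ends the records authorization under either route, which matters because annotation is part of the primary objective, and it can end the samples as well. The keep rule in 5.9 governs unclear requests only; a clear destroy request is honoured for whatever remains in the bank.

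**Conclusion.** No change is needed. The reasoning behind 20,000 is thin and its terms are loose, but no figure is shown to be wrong. The apparent surplus of up to 10,000 participants rests on an unstated target of 10,000, an assumed destroy share and attrition held at its minimum. It falls to 0 at a destroy share of 1, and becomes a shortfall if attrition is higher (40,000 needed against 20,000 at 75% attrition and full destruction).

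An amendment would define *discontinue*, state a retained target and align the wording on design and duration. The number could stay at 20,000 throughout, on the grounds of volume and diversity that the same paragraph already gives. That would be clearer text, at the price of IRB review, with nothing different done or analysed.

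The remark about statistical significance concerns clients' future studies, not a test within this one. An open control count is natural for a bank that collects on request, and the significance claim drives no decision here. The conclusion assumes that the repository tests no hypothesis of its own, as its objectives indicate, and that the hour or two describes enrolment with the required collection. It takes no position on the collection schedule.
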